### *Objectives 3–4*

For primary care data sources, the study population will include all individuals who initiate immunoglobulin treatment with prespecified immunoglobulin brands and are present in the data source during the study period. Individuals are required to have 180 days data visibility prior to study inclusion and should not have a record of an immunoglobulin prescription in the 180 days prior to study inclusion. To ensure sufficient follow-up time, only individuals who initiated immunoglobulin treatment at least 180 days before the end of the available data will be included.

For hospital care data settings, the study population will include all individuals who have an immunoglobulin record and are present in the data source during the study. Individuals are not required to have prior data availability, and no washout period will be applied prior to study inclusion. To ensure sufficient follow-up time, only individuals who initiated immunoglobulin treatment at least 180 days before the end of the available data will be included.

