#### *Objectives 3–4*

##### Inclusion criteria

- Present in the data source during the period of 01/01/2017 to 31/12/2024.
- Minimum 180 days of available history before index data. This criterion does not apply for hospital data source CDW Bordeaux.
- First drug prescription or dispensing record of prespecified immunoglobulin brand during the study period.
- No prior immunoglobulin exposure in the 180 days prior to the index date. This criterion does not apply for hospital data source CDW Bordeaux.

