### 8.6.3. Covariates, including confounders, effect modifiers, and other variables

The variables for *objective 1* are as follows:

- Calendar period
  - Year
- Route of administration:
  - Intravenous
  - Subcutaneous
  - Intramuscular
  - Other
  - Missing
- Age groups, defined at cohort entry date:
  - Overall population
  - 1 to 18 years
  - 19 to 65 years
  - >65 years and older
- Sex, defined at cohort entry date:
  - Overall
  - Male
  - Female

The variables for *objective 2* are as follows:

- Calendar period
  - Quarter of year
- Prespecified brands, including (if available):
  - Flebogamma DIF
  - Kiovig
  - Privigen
  - Octagam (5% and 10%)
  - Yimmugo
  - Ig vena
  - Intratect
  - Iqymune
  - Panzyga/Globiga
  - Gamunex
  - Hizentra
  - Hyqvia
  - Cuvitru
  - Cutaquig
  - Xembify
  - Gammagard
  - Nanogam/Optiglobin
  - Clairyg
  - Tegeline
  - Pentaglobin
  - Keycute/Naxiglo
  - Gammaplex
  - Beriglobin
  - Rhesonativ
  - Rhophylac

The variables for characterisation of immunoglobulin users (*objective 4*) are as follows:

- Demographics, at index date:
  - Sex: Female/male
  - Age
  - Age group: 1 to 18 years, 19 to 65 years, >65 years and older

- Indication for use: Prespecified conditions will be used as proxies to assess the indication for immunoglobulin use, including both authorised and non-authorised indications. The assessment windows will be any time prior to 7 days after the index date [-inf, +7], 30 days prior to 7 days after the index date [-30, +7], and 7 days prior to 7 days after the index date [-7, +7].
  - Primary immunodeficiency syndrome, including:
    - Primary immunodeficiency syndromes
  - Secondary immunodeficiencies, including:
    - Secondary immunodeficiencies
  - Neurology, including:
    - Guillain Barré syndrome (GBS)
    - Chronic inflammatory demyelinating polyradiculoneuropathy (CIDP)
    - Multifocal motor neuropathy (MMN)
    - Myasthenia gravis
    - Stiff person syndrome
    - Lambert-Eaton myasthenia syndrome
  - Haematology, including:
    - Immune thrombocytopenia (ITP)
    - Acquired von Willebrand disease
    - Foetal Neonatal Alloimmune Thrombocytopenia (FNAIT)
  - Infectious diseases, including:
    - Measles
  - Solid organ transplantation, including:
    - Transplantation
  - Internal medicine, including:
    - Kawasaki's disease
    - Inflammatory myopathy
    - (Juvenile) dermatopolymyositis
    - ANCA vasculitis (replacement therapy)
    - Systemic lupus erythematosus (SLE)

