To ensure comprehensive characterisation of all incident individuals, a minimum of 180 days of prior data availability is required for primary care data sources. This criterion may reduce the study size and will not be applied for hospital-based settings, where patients typically seek care for acute or specialised conditions and might, as a result, not have a long duration of longitudinal registration, as would be expected in a primary care setting data sources. Consequently, for CDW Bordeaux, it is uncertain whether included individuals are true incident users. Moreover, only a subset of included patients from hospital-based settings may contribute to time windows prior to the index date. The prior observation requirement may also imply selection bias favouring chronic indications, i.e., data in some pathological conditions may be limited or absent.

Of note, certain brands of interest cannot be assessed in the current study due to limitations, such as market authorisation occurring after the study period or the unavailability of an RxNorm code for those specific brands.

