#### **United Kingdom: Clinical Practice Research Datalink GOLD (CPRD GOLD)**

CPRD GOLD will be included in this study because it is a primary care data source that provides relevant information on the use of immunoglobulins in the general population.

Based on a preliminary feasibility assessment, the expected number of person counts for immunoglobulin use in CPRD GOLD will be 73,600.

Moreover, data availability and follow-up in CPRD GOLD is sufficient, as data availability starts in 1987, and the date of most recent data extraction is 05/2025, which aligns with the study period. The median follow-up of the first observation period is 2,150 days.

There are no study specific limitations present in CPRD GOLD.

Lastly, CPRD GOLD has blanket approval, which makes the execution of this study feasible within the current study timelines.

Table S1. Fitness-for-use assessment of data sources.

Design elements	Operational definition	Data elements for valid capture	Criticality of the quality of the element, including justification where relevant	Suggested extensiveness assessment	Suggested assessment of other quality dimensions	Suggested substantiation by documentation
Study population	General study population ( obj. 1 )	N/A	N/A	N/A	N/A	N/A
	Population with an immunoglobulin prescription ( obj. 2–4 )	Prescription of immunoglobulin treatment (RxNorm code)	High	100% will have an immunoglobulin prescription, the expected number of persons counts for immunoglobulins in the data sources included in this study range from 10,900 (CDW Bordeaux) to 73,600 (CPRD GOLD).	100% of prescriptions have been mapped to RxNorm	N/A
Treatment/exposure	Immunoglobulin prescription	Prescription of immunoglobulin treatment (RxNorm code)	High	N/A (to be assessed on a research question basis)	N/A	N/A
Comparator group (not relevant)	N/A	N/A	N/A	N/A	N/A	N/A
Key outcomes per objective	Immunoglobulin prescription ( obj. 1 )	Prescription of prespecified immunoglobulin treatment (RxNorm code), including, if available, route of administration	Medium	Immunoglobulin prescriptions are included in all data sources. The expected number of persons counts for immunoglobulins in the data sources included in this study range from 10,900 (CDW Bordeaux) to 73,600 (CPRD GOLD).	N/A	N/A

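### Users with no identifiable prespecified brand have no row in objective 2 and go undescribed in objectives 3 and 4, so brand shares can move for reasons unrelated to any brand

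*Protocol*

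**What the plan says.** **Brand identification.** Section 9 states that "certain brands of interest cannot be assessed in the current study due to limitations". It gives two examples of such limitations: authorisation after the study period, and "the unavailability of an RxNorm code for those specific brands". Section 8.6.3 lists 25 brand entries for objective 2, qualified as applying where available, with no other, unspecified or missing category. In the same section, the route variable of objective 1 has both an Other and a Missing category.

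**Objective 2 population.** The abstract admits anyone with an immunoglobulin record. Section 8.8.3 divides by the prevalent immunoglobulin users of the quarter. Section 8.3 instead requires a record of a prespecified brand.

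**Objectives 3 and 4.** Section 7 words objective 3 for immunoglobulin use generally. Section 8.3 sets entry at "First drug prescription or dispensing record of prespecified immunoglobulin brand during the study period", and section 8.8.3 and mock Tables 3 to 8 report per brand. For the hospital source, the abstract instead admits any immunoglobulin record. For primary care, individuals "should not have a record of an immunoglobulin prescription in the 180 days prior to study inclusion". That washout counts any immunoglobulin, branded or not.

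**Completeness.** In Annex II, Table S1, the row for the population with an immunoglobulin prescription says "100% of prescriptions have been mapped to RxNorm". The brand-specific rows for objectives 2 and 3 give no figure and mark the assessment as not applicable, to be made per research question.

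**The concern.** Objective 2 exists to show the distribution and quarterly trend of brands. If the denominator holds people who cannot appear in any brand numerator, each share depends on how many such people there are in the quarter. A season with more use of a monoclonal antibody, or a change in how often records carry a brand, would move all brands together and could be read as a market change. Without a residual row, the tables cannot show that this has happened.

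In objectives 3 and 4, the dose, duration, indication and infection results describe only people whose brand is identifiable, although objective 3 reads as covering immunoglobulin use at large. In primary care a second loss follows: an unbranded immunoglobulin record can disqualify a person at a later branded record.

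**Working it through.** The protocol states no figure for brand completeness, so there is nothing to reproduce. The check compares its lists and then shows how a share responds.

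**1. Brand list against code list.** Section 8.6.3 has 25 entries. Table S4 has concepts for 24 of them, and the one without is "Keycute/Naxiglo". The protocol does not say which of its two reasons applies to this entry. If the product was not marketed in the period, its absence does no harm.

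**2. Ingredients against brands.** Table S3 lists 42 immunoglobulin ingredients. One is under J06B, ten under J06BA and one under J06BB01, which makes 12. The other 42 − 12 = 30 (J06BB02 to J06BD09: specific immunoglobulins, antitoxins, immunosera and monoclonal antibodies) match no brand in Table S4. If the denominator follows Table S3, users of only these 30 can never enter a brand numerator, even with perfect coding.

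**3. Effect on a share.** Let *p* be the true share and *c* the fraction of users whose brand is identifiable. Take *p* = 30% and *c* from 100% down to 50%; both are assumptions.

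- All-user denominator: observed share = *p* × *c*.
- Brand-identified denominator, all brands affected alike: *p* × *c* / *c* = *p*.
- Brand-identified denominator, only this brand affected: *p* × *c* / (*p* × *c* + 0.70).

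| *c* | All users | Brand-identified, equal loss | Brand-identified, this brand only |
|---|---|---|---|
| 100% | 30% | 30% | 30% |
| 90% | 27% | 30% | 27.8% |
| 80% | 24% | 30% | 25.5% |
| 70% | 21% | 30% | 23.1% |
| 50% | 15% | 30% | 17.6% |

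The choice between the abstract and section 8.8.3 on one side and section 8.3 on the other therefore decides whether a common shift reaches the results.

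**4. Scale for objectives 3 and 4.** The only counts are the feasibility figures for any immunoglobulin. If 5% to 50% lack an identifiable brand (assumed), the numbers would be:

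- CDW Bordeaux: 0.05 × 10,900 = 545 to 0.50 × 10,900 = 5,450
- IQVIA DA Germany: 0.05 × 47,500 = 2,375 to 0.50 × 47,500 = 23,750
- CPRD GOLD: 0.05 × 73,600 = 3,680 to 0.50 × 73,600 = 36,800

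These bases are not initiators within the study period, so they show scale only.

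**5. Washout in primary care.** Suppose that a person has an unbranded record on day 0 and the first branded record on day 100. The index date is the branded record. The washout covers the 180 days before it and counts any immunoglobulin, so the person fails. Later branded records are not the first in the study period, so the criteria as written give no second entry. The attrition shell (mock Table 2) has a general immunoglobulin step and a washout step, but none for brand identification.

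**The case against.** The strongest reply is that section 9 describes a fixed gap for certain products and discloses it. Only one listed entry lacks a concept, and Annex I says that German prescriptions are recorded at product-code level. Code lists are preliminary and will be refined, and sections 8.1 and 8.6.2 scope objectives 3 and 4 to prespecified brands. Much of this stands. It limits how large the problem need be, but it does not give the remaining users a row or settle the denominator. The variable list and table shells are already fixed in this document, so the gap is not merely detail left for later.

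A reader might also infer stronger claims that the documents do not support:

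- **That brand coding changed over the period.** No section says so. A shift from coding is possible, not shown.
- **That Table S1 contradicts section 9.** The 100% cell belongs to the row for any immunoglobulin prescription, and the brand rows make no claim. The fair criticism is that the figure says nothing about brand.
- **That cohort entry needs a person's very first record to carry a brand.** The hospital source has no washout, and in primary care an unbranded record more than 180 days earlier does not block entry.
- **That the unidentified fraction in objective 2 equals the loss in objectives 3 and 4.** One is a share of quarterly users and the other of initiators, and people with mixed records may still enter.

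**Conclusion.** The point holds in limited form. By the protocol's own account, brand identification is incomplete, and 30 of 42 ingredients correspond to no prespecified brand. Under the all-user denominator, these users count below the line and in no row, so changes in their number can move every brand share. Under a brand-identified denominator, a shift common to all brands cancels, but a brand-specific one does not. The protocol supports both readings and must choose.

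For objective 3, the wording and the output do not match: users without an identifiable brand are not described, and in primary care some branded users are lost through the washout. The hospital entry rule in the abstract conflicts with section 8.3, but the results are tabulated by brand either way.

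The size cannot be stated, because it rests on brand-level completeness that the documents do not give. The 30% share and the completeness range are illustrations. The conclusion also assumes that Tables S3 and S4, both preliminary, define the immunoglobulin denominator and the brands. The change is worth making before the analysis code is run, because it decides what the trends can be taken to mean.

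**What to change.** 1. **Reconcile the populations.** Bring the abstract and section 8.8.3 into line with section 8.3 for objective 2, and the abstract into line with section 8.3 for the hospital source in objectives 3 and 4. Fix one objective 2 denominator, preferably users of the ingredients to which the prespecified brands belong.
2. **Add residual categories to objective 2, by quarter and source.** Keep two groups apart: brand not identified (normal and anti-D immunoglobulin), and other immunoglobulin with no prespecified brand. Pooling them would hide coding gaps behind use of unrelated products. If the denominator is restricted as in item 1, report the second group as a count beside the table.
3. **Describe the omitted users in objectives 3 and 4.** Add an overall or brand-not-identified cohort, and add a brand-identification step to the attrition table. Do not move the index date back to an unbranded record on condition that a branded one follows, because that would define entry by future information.
4. **Report brand mapping.** Give the percentage of immunoglobulin records mapped to a brand concept, per source and calendar period, alongside the general figure in Table S1.

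The cost is a few table rows, one cohort and one mapping count per source. No new data are needed.

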## 11. ANNEXES

### ANNEX I. Description of data sources

#### DATA SOURCES DESCRIPTION

##### France: Clinical Data Warehouse of Bordeaux University Hospital (CDW Bordeaux)

#	Section	Description
1	Database Identification and country	CDW Bordeaux (Clinical Data Warehouse of Bordeaux University Hospital) Nouvelle-Aquitaine, France
2	Data partner information section	CHU DE BORDEAUX - DIRECTION GENERALE Gironde / Nouvelle-Aquitaine
3	Coverage and timespan	Data collection since 2005 Extent: Regional. It covers the population of Bordeaux metropolitan area, and possibly beyond, as the health care centre for referrals and expertise for the Nouvelle Aquitaine region. The database contains data from 2005 onwards.
4	Healthcare setting / type of data	Secondary care – specialists (ambulatory or hospital outpatient care), and hospital inpatient care, and claims data. The database currently captures information about patient demographics, visit details, conditions, procedures, drugs, measurements, and mortality.
5	Data collection process	Outpatient electronic health records, and Inpatient hospital electronic health records, and Inpatient hospital billing systems, and Biobank. The integrated data is extracted from the hospital production information system via a real-time research database. The data is then processed and quality controlled by a team dedicated to maintaining the database. Internal evaluations were carried out to ensure consistency between the research database and the patient bedside software.
6	General representativeness	This is the 6th largest metropolitan area in France, and CHUBX is the largest hospital in the region. More than 75% of the patients administered to Bordeaux university hospital reside in the Gironde departments, with almost 50% coming directly from the Bordeaux metropolitan area. The hospital also captures additional cases from Nouvelle-Aquitaine region.
7	Data content /source coding	Diagnosis source data is coded in ICD-10 terminology. Procedures are coded in CCAM (French terminology). Laboratory measurements are coded in local terminology and partially mapped to LOINC. Drugs are coded through a local terminology and then mapped to UCD (French terminology), as well as ATC codes.
8	Data Harmonization	The data has been mapped to the OMOP CDM v5.4 and the OMOP standard vocabularies (SNOMED, RxNorm, LOINC). The format, structural and semantic conformance has been verified upon onboarding into the DARWIN EU® data network. We use the hospital's unique identifier to generate the patient identifier in OMOP. If two identities are merged at the hospital, the merge is taken into account in the CDW. An automatic (hourly) detection of suspected duplicated identities has been implemented at the hospital since 2020, with merging of duplicated identities by a specialised team. Identities since 2015 were processed retrospectively. Thus, the rate of identity duplication in the database is low, especially since 2015.
9	Quality control (database specific)	- The integrated data comes from the hospital production information system through a real-time replicated database. Consistency evaluations between the replicated database and the production system are performed by the technical team in charge of maintaining the replicated database. - In the same way, consistency checks are performed between the replicated database and the data integrated into the i2b2 CDW. In addition, dashboards enable monitoring the data integrated into the i2B2 CDW, in particular by controlling the amount of data available over time, and its evolution, according to the various data sources. - An internal evaluation was carried out to ensure the consistency between the data integrated

#	Section	Description
		into i2b2 and the data available in the software used at the patient's bedside. In addition, many use cases were performed on the i2b2 CDW, with return to the patient chart and comparison of the data integrated into i2b2 and the data available in the care file.
10	Linkage	Death certificates (without the cause of death).
11	Vital status	The database is linked to the French death registry.
12	Limitations	CDW Bordeaux is limited to events captured in the hospital setting and thus does not include patient events not treated by the hospital (e.g. rare cancers). Patient events that are not included in CDW Bordeaux are rare disease treatments or specialist events that occur outside of CHUBX.
13	Main references	Cossin S, Diouf S, Griffier R, Le Barrois d'Orgeval P, Diallo G, Jouhet V "Linkage of Hospital Records and Death Certificates by a Search Engine and Machine Learning." JAMIA open (2021): 33709061
14	Link to HMA-EMA catalogue and database webpage	HMA-EMA Catalogue entry: https://catalogues.ema.europa.eu/data-source/1111112 Website: https://www.chu-bordeaux.fr/

Germany: IQVIA Disease Analyzer Germany (IQVIA DA Germany)

#	Section	Description
1	Database Identification and country	IQVIA DA Germany (IQVIA Disease Analyzer Germany) Germany
2	Data partner information section	IQVIA
3	Coverage and timespan	Data collection since 1989 Extent: Nation-wide. GP and specialists in Germany using specific patient management software.
4	Healthcare setting / type of data	Primary care – gps, and primary care specialists (e.g. paediatricians). Diagnoses, medication, and procedures from an ambulatory setting. Medications are recorded as prescriptions of marketed products.
5	Data collection process	Outpatient electronic health records. By clinicians at healthcare contact.
6	General representativeness	No specific details on general representativeness given.
7	Data content /source coding	Prescription is on product code level (German PZN), ICD10, NFC, Local lab coding.
8	Data Harmonization	The data has been mapped to the OMOP CDM v5.4 and the OMOP standard vocabularies (SNOMED, RxNorm, LOINC). The format, structural and semantic conformance has been verified upon onboarding into the DARWIN EU® data network. There can be patients registered under different ID numbers, because there is no linkage between different GPs.
9	Quality control (database specific)	Data is quality checked on plausibility.
10	Linkage	No.
11	Vital status	Death information is derived from medical events.
12	Limitations	No database-specific limitations documented. General limitations for the data type applicable.
13	Main references	No main reference provided.

#	Section	Description
14	Link to HMA-EMA catalogue and database webpage	HMA-EMA Catalogue entry: https://catalogues.ema.europa.eu/data-source/104282 Website: https://www.iqvia.com/

United Kingdom: Clinical Practice Research Datalink GOLD (CPRD GOLD)

#	Section	Description
1	Database Identification and country	CPRD GOLD (Clinical Practice Research Datalink GOLD ) United Kingdom
2	Data partner information section	University of Oxford NDORMS
3	Coverage and timespan	Data collection since 1987 Extent: Nation-wide. CPRD GOLD consists of patients in contributing practices using Vision software. Historically this covered the whole of the UK, but the number of contributing practices in the England is dropping. In January 2025 only 3 practices from England were a part of CPRD GOLD, while historical patient data were from the whole of the UK, and will continue to be so. In the future, no practices from England will be present, only practices from Scotland, Wales, and Northern Ireland.
4	Healthcare setting / type of data	Primary care – gps, and primary care specialists (e.g. paediatricians), and secondary care – specialists (ambulatory or hospital outpatient care), and hospital inpatient care. CPRD GOLD data include patient demographics, biological measurements, clinical symptoms and diagnoses, referrals to specialist/hospital and their outcome, laboratory tests/results, and prescribed medications.
5	Data collection process	Outpatient electronic health records. Data is entered by clinicians into the EHR. Data is processed by CPRD and provides data releases for research.
6	General representativeness	CPRD GOLD has been assessed and found to be broadly representative of the UK general population in terms of age, gender, and ethnicity. In CPRD GOLD in January 2025 there were 2,730,707 current acceptable patients (i.e. registered at currently contributing practices that use Vision software, excluding transferred out, deceased patients, and those flagged by CPRD as not acceptable for clinical research for data quality issues). This equals to 4.07%, based on the UK population estimates of 67,026,300 from the Office of National Statistics (mid-2023). Current patients are only from Scotland, Wales, and Northern Ireland. Historically, GOLD does contain data from England as well.
7	Data content /source coding	Gemsript, Read, dm+d
8	Data Harmonization	The data has been mapped to the OMOP CDM v5.4 and the OMOP standard vocabularies (SNOMED, RxNorm, LOINC). The format, structural and semantic conformance has been verified upon onboarding into the DARWIN EU® data network. In GOLD, a patient can be registered under different ID numbers upon changing practice or re-registration. Researchers are not able to identify these patients, as the data are anonymised. However, GOLD covers less than 5% of the current UK GP practices and it is unlikely that an individual who does change GP practice ends up in another GP practice which uses the Vision software and accepts the CPRD data collection agreement. The very small number of duplicated IDs will have different observation periods and should not have an impact on the data analyses.
9	Quality control (database specific)	CPRD GOLD only includes practices whose data quality is assessed to be up-to-standard (uts). Each practice is associated to an uts date set when the data quality standards become satisfactory, and CPRD recommend using only longitudinal data starting from this uts date. Every time CPRD collect the EHR from a practice, checks are run for the data quality standards and if they are not adequate, the EHR is not accepted. When the data quality becomes acceptable again, CPRD updates the practice uts date. CPRD also check data quality standards at the patient

#	Section	Description
		level and associate each patient to a flag, reporting if its data is acceptable for clinical research. Only patients with acceptable data quality are included in the population to be mapped to CDM.
10	Linkage	CPRD GOLD can be linked to several sources, however our Oxford OMOP CDM is only linked to the CPRD GOLD Ethnicity Record and to the CPRD Townsend Deprivation Index at Practice Level
11	Vital status	Vital status is retrieved from the GP records. Population registry (ONS) data can be requested on a study-by-study basis and linked. This data only covers England and is planned to be mapped to OMOP in the future. The cause of death is not captured.
12	Limitations	The main limitation is due to the fact that CPRD GOLD is limited to GP records, and although it contains information on referrals and discharge letters, it may not fully capture specific hospital information. Events from hospital and specialist care are not covered.
13	Main references	Sanchez-Santos MT, Axson EL, Dedman D, Delmestri A "Data Resource Profile Update: CPRD GOLD." International journal of epidemiology (2025): 40499193
14	Link to HMA-EMA catalogue and database webpage	HMA-EMA Catalogue entry: https://catalogues.ema.europa.eu/data-source/1111113 Website: https://cprd.com

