### 8.8.3. Statistical model specification and assumptions of the analytical approach considered

#### Objective 1

Trends of immunoglobulin use during the study period will be assessed based on OMOP CDM mapped data using the *IncidencePrevalence* R package (<https://github.com/darwin-eu/IncidencePrevalence>), developed by DARWIN EU®.

The prevalence of individuals with a recorded immunoglobulin prescription (expressed as the proportion of individuals with any immunoglobulin prescription in the general study population) will be presented by immunoglobulin ingredient, route of administration, and stratified by sex and age.

Prevalence will be calculated as overall and annual, which summarises the total number of individuals with recorded immunoglobulin use during a given period divided by the population at risk of receiving immunoglobulins during that period. Therefore, period prevalence will give the proportion of individuals exposed at any time during a specified interval. Binomial 95% confidence intervals will be calculated.

#### Objective 2

Trends of immunoglobulin use during the study period will be assessed based on OMOP CDM mapped data using the *IncidencePrevalence* R package (<https://github.com/darwin-eu/IncidencePrevalence>), developed by DARWIN EU®.

The quarterly prevalence of individuals with prescriptions for prespecified immunoglobulin brands will be estimated (expressed as the proportion of individuals prescribed each specific immunoglobulin brand among prevalent immunoglobulin users).

Prevalence will be calculated as quarterly period prevalence, which summarises the total number of individuals with recorded immunoglobulin brand prescription during a quarter divided by the population of prevalent immunoglobulin users during that period. Therefore, period prevalence will give the proportion of individuals exposed to a specific brand at any time during the specified interval. Binomial 95% confidence intervals will be calculated.

An illustration of the calculation of period prevalence is shown below in **Figure 3**. Between time  $t+2$  and  $t+3$ , two of the five study participants receive immunoglobulin treatment, giving a prevalence of 40%. Meanwhile, for the period  $t$  to  $t+1$  all five also had some observation time during the year with one of the five study participants having a recorded immunoglobulin prescription, giving a prevalence of 20%.

[figure not shown]

Figure 3. Prevalence example.

### Objective 3

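### CPRD GOLD has been losing its English practices, so its 2017–2024 trends cannot be separated from a change in who contributes, and the plan does not address this

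*Protocol*

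**What the plan says.** Annex I, in the CPRD GOLD row on coverage and timespan, describes a source whose geography is changing: "Historically this covered the whole of the UK, but the number of contributing practices in the England is dropping". It then gives the position just after the study period: "In January 2025 only 3 practices from England were a part of CPRD GOLD, while historical patient data were from the whole of the UK". The row on representativeness adds: "Current patients are only from Scotland, Wales, and Northern Ireland".

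The study period runs from 01/01/2017 to 31/12/2024 (Section 8.5). Objective 1 asks for overall and annual prevalence, and objective 2 for quarterly brand trends among immunoglobulin users (Section 7). For both, Section 8.8.3 states: "Trends of immunoglobulin use during the study period will be assessed based on OMOP CDM mapped data". The objective 1 population is everyone present in the source, with no exclusions (Section 8.3). Its planned breakdowns are ingredient, route, age and sex; objective 2 has calendar quarter and brand (Sections 8.6.3 and 8.8.3).

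Section 9 names care setting and the way each source defines observation time as influences on the prevalence population. It says nothing about practices leaving CPRD GOLD. Annex II concludes: "There are no study specific limitations present in CPRD GOLD".

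**The concern.** The denominator of each annual or quarterly estimate is whoever CPRD GOLD holds in that period. As English practices leave, the mix moves towards Scotland, Wales and Northern Ireland. If GP-recorded immunoglobulin use or brand mix differs between nations, the pooled series will rise or fall even when use within every nation is constant. Age and sex strata do not remove this, and binomial confidence intervals do not reflect it.

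What is at stake is how the CPRD GOLD curves are read. A reader of the report would have no means of telling a change in use from a change in contributors, and Annex II would suggest that there is nothing to look for.

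**Working it through.** **The protocol's own figure.** Annex I gives 2,730,707 current patients and a UK population of 67,026,300. 2,730,707 / 67,026,300 = 4.074%, which matches the stated 4.07%. This is coverage in January 2025. It says nothing about 2017 or about the split by nation.

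**What the protocol gives and does not give.**
- Given: an ongoing fall in English practices, 3 left in January 2025, a study period ending the month before, and open inclusion of everyone present.
- Not given: the English share of patients in any year, when the practices left, or immunoglobulin use by nation.

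That some of the loss falls within 2017–2024 is an inference from a decline described as still under way. Its size cannot be computed from the protocol, so it can only be illustrated.

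**Illustration.** Let w be the assumed English share of the 2017 denominator, falling to about 0 in 2024. Let r be the assumed ratio of English prevalence to prevalence in the other nations. Hold use constant within each nation and set prevalence outside England to 1.

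- Pooled 2017 value = w·r + (1 − w)
- Pooled 2024 value = 1
- Spurious relative change = 1 / (w·r + 1 − w) − 1

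| w | r = 0.5 | r = 0.75 | r = 1 | r = 1.25 |
|---|---|---|---|---|
| 10% | 1/0.950 − 1 = +5.3% | 1/0.975 − 1 = +2.6% | 0 | 1/1.025 − 1 = −2.4% |
| 20% | 1/0.900 − 1 = +11.1% | 1/0.950 − 1 = +5.3% | 0 | 1/1.050 − 1 = −4.8% |
| 40% | 1/0.800 − 1 = +25.0% | 1/0.900 − 1 = +11.1% | 0 | 1/1.100 − 1 = −9.1% |
| 60% | 1/0.700 − 1 = +42.9% | 1/0.850 − 1 = +17.6% | 0 | 1/1.150 − 1 = −13.0% |

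The same formula serves objective 2 if w is read as the English share of immunoglobulin users and r as the ratio of brand shares.

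**Would sampling error hide it?** Table 1 of Section 8.4 gives 2,632,700 active individuals, used here as a rough yearly denominator. With p the assumed prevalence, the 95% half-width relative to the estimate is 1.96·√(p(1 − p)/2,632,700)/p. This is 5.4% at p = 0.05%, 3.8% at 0.1% and 2.2% at 0.3%. For the all-ages, all-ingredient annual series, a moderate shift in composition could therefore look like a precisely estimated trend. Strata and single brands will be noisier.

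**The case against.** The strongest reply is that the size of the problem rests wholly on assumption. Annex I contrasts an unspecified past, in a source collecting since 1987, with January 2025. If most English practices left before 2017, little of the shift falls in the study period. Nothing in the protocol says that GP immunoglobulin prescribing or brand supply differs between UK nations, and without a difference there is no distortion. All of this stands. It limits the claim to what cannot be separated; it does not show that the trends can be separated.

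Second, Annex I discloses the change openly, and the Annex II sentence is repeated for all three sources. A reader might infer that Annex II denies the shift. It does not: it says only that no limitation is specific to this study. But calendar trend is an objective here, so a changing panel is a limitation for this study, and the sentence does not fit with Annex I.

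Third, a reader might infer that the series will be offered as the trend of the United Kingdom. The protocol reports by data source, plans no meta-analysis, and says in Section 9 that results reflect only the populations captured. The country label identifies the source.

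Fourth, replacing the all-practice series with a fixed panel would change the objective 1 population and bring its own selection. That also stands, and argues for a companion series and not a new main analysis.

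**Conclusion.** The point holds as a limit on interpretation. As planned, a change over time in CPRD GOLD prevalence or brand share cannot be separated from the change in contributing practices, and neither the analysis, Section 9 nor Annex II deals with it. Under an assumed 2017 English share of 10–60%, falling to about zero by 2024, and an assumed prevalence ratio of 0.5–1.25, the spurious change lies between about −13% and +43%. It is zero at a ratio of 1. None of these inputs comes from the protocol.

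A reader might go further and conclude that the CPRD GOLD trends are biased, or biased by a known amount. The protocol does not support that, since both the timing of the loss and any difference between nations are missing. Nor should the 73,600 expected users be taken as the sample behind the trend: that feasibility count carries no calendar window. The overall period prevalence does not depend on a trend and is not the target of this point. The matter is a cheap improvement affecting one source of three and two objectives of four.

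**What to change.** Keep the all-practice series as planned. In Section 8.8.3, add for CPRD GOLD a companion annual series (objective 1) and quarterly series (objective 2), restricted either to Scottish, Welsh and Northern Irish practices or to practices contributing throughout 2017–2024. Report yearly denominators by nation beside both series.

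Confirm first that the OMOP extract holds nation or practice identifiers. Annex I mentions linkage to a deprivation index at practice level, which suggests that such a field may exist but does not establish it. If it does not, state in Section 9 and in the report that CPRD GOLD trends cannot be read as changes in UK use.

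In either case, correct the Annex II sentence and add the shift to Section 9. Annex I should also be reconciled with itself: it counts 3 English practices in January 2025, yet places all current patients outside England.

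The text changes cost almost nothing. The companion series costs one extra run in one source. Its early denominators will be smaller, it gives no English trend if restricted by nation, and a panel of continuously contributing practices may be selected.
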